9.1.2 Withdrawal of informed consent

Subjects may voluntarily withdraw consent to participate in the study for any reason at any time. Withdrawal of consent (WoC) occurs only when a subject:

- Does not want to participate in the study anymore

and

- Does not allow further collection of personal data

In this situation, the investigator should make a reasonable effort (e.g. telephone, e-mail, letter) to understand the primary reason for the subject's decision to withdraw his/her consent and record this information.

Study treatment must be discontinued and no further assessments conducted, and the data that would have been collected at subsequent visits will be considered missing.

Further attempts to contact the subject are not allowed unless safety findings require communicating or follow-up.

All efforts should be made to complete the assessments prior to study withdrawal. A final evaluation at the time of the subject's study withdrawal should be made as detailed in the assessment table.

Novartis will continue to keep and use collected study information (including any data resulting from the analysis of a subject's sample until the time of withdrawal) according to applicable law.

All biological samples not yet analyzed at the time of withdrawal may still be used for further testing/analysis in accordance with the terms of this protocol and of the informed consent form.

9.1.3 Lost to follow-up

For subjects whose status is unclear because they fail to appear for study visits without stating an intention to discontinue or withdraw, the investigator must show "due diligence" by documenting in the source documents steps taken to contact the subject, e.g. dates of telephone calls, registered letters, etc. A subject should not be considered as lost to follow-up until due diligence has been completed. Follow-up is recommended until the end of the study.

9.1.4 Early study termination by the sponsor

The study can be terminated by Novartis at any time.

Reasons for early termination:

- Unexpected, significant, or unacceptable safety risk to subjects enrolled in the study
- Decision based on recommendations from applicable board(s) after review of safety and efficacy data
- Discontinuation of study drug development

In taking the decision to terminate, Novartis will always consider the subject's welfare and safety. Should early termination be necessary, subjects must be seen as soon as possible and treated as a prematurely withdrawn subject. The investigator may be informed of additional procedures to be followed in order to ensure that adequate consideration is given to the protection of the subject's interests. The investigator or sponsor, depending on the local regulation, will be responsible for informing IRBs/IECs of the early termination of the trial.

9.2 Study completion and post-study treatment

Study completion is defined as when the last subject finishes their Study Completion visit, and any repeat assessments associated with this visit have been documented and followed-up

appropriately by the Investigator, or in the event of an early study termination decision, the date of that decision.

Patients will be eligible for post-trial access after completion of the study.

10 Safety monitoring and reporting

10.1 Definition of adverse events and reporting requirements

10.1.1 Adverse events

An adverse event (AE) is any untoward medical occurrence (e.g., any unfavorable and unintended sign [including abnormal laboratory findings], symptom or disease) in a subject or clinical investigation subject after providing written informed consent for participation in the study. Therefore, an AE may or may not be temporally or causally associated with the use of a medicinal (investigational) product.

The investigator has the responsibility for managing the safety of individual subject and identifying adverse events.

Novartis qualified medical personnel will be readily available to advise on trial related medical questions or problems.

The occurrence of adverse events must be sought by non-directive questioning of the subject at each visit during the study. Adverse events also may be detected when they are volunteered by the subject during or between visits or through physical examination findings, laboratory test findings, or other assessments.

Adverse events must be recorded in the appropriate CRF under the signs, symptoms or diagnosis associated with them, accompanied by the following information (as far as possible) (if the event is serious refer to [Section 10.1.2](#)):

1. The Common Toxicity Criteria (CTC) AE grade (version 5 or higher);
2. its relationship to the study treatment and other investigational treatment. If the event is due to lack of efficacy or progression of underlying illness (i.e. progression of the study indication) the assessment of causality will usually be 'Not suspected'. The rationale for this guidance is that the symptoms of a lack of efficacy or progression of underlying illness are not caused by the trial drug, they happen in spite of its administration and/or both lack of efficacy and progression of underlying disease can only be evaluated meaningfully by an analysis of cohorts, not on a single subject;
3. its duration (start and end dates) or if the event is ongoing, an outcome of not recovered/not resolved must be reported;
4. whether it constitutes a SAE (see [Section 10.1.2](#) for definition of SAE) and which seriousness criteria have been met;
5. action taken regarding with study treatment.

All adverse events must be treated appropriately. Treatment may include one or more of the following:

- Dose not changed

- Dose reduced/increased
- Drug interrupted/withdrawn
- 6. its outcome i.e., its recovery status or whether it was fatal.

Conditions that were already present at the time of informed consent should be recorded in medical history of the subject.

Adverse events (including lab abnormalities that constitute AEs) should be described using a diagnosis whenever possible, rather than individual underlying signs and symptoms.

Adverse event monitoring should be continued for at least 30 days following the last dose of study treatment or end of study visit, whichever is longer.

Once an adverse event is detected, it must be followed until its resolution or until it is judged to be permanent (e.g. Continuing at the end of the study), and assessment must be made at each visit (or more frequently, if necessary) of any changes in severity, the suspected relationship to the interventions required to treat it, and the outcome.

Information about adverse drug reactions for the investigational drug can be found in the Investigator Brochure (IB).

Abnormal laboratory values or test results constitute adverse events only if they fulfill at least one of the following criteria:

- they induce clinical signs or symptoms
- they are considered clinically significant
- they require therapy

Clinically significant abnormal laboratory values or test results must be identified through a review of values outside of normal ranges/clinically notable ranges, significant changes from baseline or the previous visit, or values which are considered to be non-typical in subjects with the underlying disease. Alert ranges for laboratory and other test abnormalities are included in [Section 16.1](#) Appendix 1.

For lab values provided without related clinical information, the Common Terminology Criteria for Adverse Events (CTCAE) scale must be used to determine the seriousness. Any value of Grade 4 and above on this CTCAE scale must be considered serious.

10.1.2 Serious adverse events

An SAE is defined as any adverse event [appearance of (or worsening of any pre-existing)] undesirable sign(s), symptom(s) or medical conditions(s)) which meets any one of the following criteria:

- fatal
- life-threatening

Life-threatening in the context of a SAE refers to a reaction in which the subject was at risk of death at the time of the reaction; it does not refer to a reaction that hypothetically might have caused death if it were more severe (please refer to the ICH-E2D Guidelines).

- results in persistent or significant disability/incapacity
- constitutes a congenital anomaly/birth defect

- requires inpatient hospitalization or prolongation of existing hospitalization, unless hospitalization is for:
 - routine treatment or monitoring of the studied indication, not associated with any deterioration in condition
 - elective or pre-planned treatment for a pre-existing condition that is unrelated to the indication under study and has not worsened since signing the informed consent
 - social reasons and respite care in the absence of any deterioration in the subject's general condition
 - treatment on an emergency outpatient basis for an event not fulfilling any of the definitions of a SAE given above and not resulting in hospital admission
- is medically significant, e.g. defined as an event that jeopardizes the subject or may require medical or surgical intervention to prevent one of the outcomes listed above

Medical and scientific judgment should be exercised in deciding whether other situations should be considered serious reactions, such as important medical events that might not be immediately life threatening or result in death or hospitalization but might jeopardize the subject or might require intervention to prevent one of the other outcomes listed above. Such events should be considered as "medically significant". Examples of such events are intensive treatment in an emergency room or at home for allergic bronchospasm, blood dyscrasias or convulsions that do not result in hospitalization or development of dependency or abuse (please refer to the ICH-E2D Guidelines).

All malignant neoplasms will be assessed as serious under "medically significant" if other seriousness criteria are not met and the malignant neoplasm is not a disease progression of the study indication.

Any suspected transmission via a medicinal product of an infectious agent is also considered a serious adverse reaction.

All reports of intentional misuse and abuse of the product are also considered serious adverse event irrespective if a clinical event has occurred or not.

10.1.3 SAE reporting

To ensure subject safety, every SAE, regardless of causality, occurring after the subject has provided informed consent and until 30 days after the last study visit must be reported to Novartis safety within 24 hours of learning of its occurrence. Any SAEs experienced after the 30 day period after the last study visit should only be reported to Novartis Safety if the investigator suspects a causal relationship to study treatment. Any SAEs reported up to the subject's last visit will be reported in the eCRF. SAEs beyond that date will only be recorded in the Novartis Safety database.

Recurrent episodes, complications, or progression of the initial SAE must be reported as follow-up to the original episode, regardless of when the event occurs. This report must be submitted within 24 hours of the investigator receiving the follow-up information. An SAE that is considered completely unrelated to a previously reported one should be reported separately as a new event.

Information about all SAEs is collected and recorded on the Serious Adverse Event Report Form; all applicable sections of the form must be completed in order to provide a clinically thorough report. The Investigator must assess the relationship of each SAE to each specific component of the study treatment (if the study treatment consists of several components) complete the SAE Report Form in English and submit the completed form within 24 hours to Novartis. Detailed instructions regarding the submission process and requirements for signature are to be found in the investigator folder provided to each site.

Follow-up information is submitted as instructed in the investigator folder. Each reoccurrence, compilation, or progression of the original event must be reported as a follow-up to that event regardless of when it occurs. The follow-up information should describe whether the event has resolved or continues, if and how it was treated, whether the blind was broken or not, and whether the patient continued or withdrew from study participation.

If the SAE is not previously documented in the Investigator's Brochure or Package Insert (new occurrence) and is thought to be related to the investigational treatment, a Chief Medical Office and Patient Safety (CMO & PS) Department associate may urgently require further information from the investigator for health authority reporting. Novartis may need to issue an Investigator Notification (IN) to inform all investigators involved in any study with the same study treatment that this SAE has been reported.

Suspected Unexpected Serious Adverse Reactions (SUSARs) will be collected and reported to the competent authorities and relevant ethics committees in accordance with EU Guidance 2011/C 172/01 or as per national regulatory requirements in participating countries.

Detailed instructions regarding the submission process and requirements are to be found in the investigator folder provided to each site.

Consider the following 3 categories (as applicable) to determine SAE reporting timeframes:

1. To ensure patient safety, every SAE, regardless of causality, occurring after the patient has provided informed consent and until 30 days after the last study visit must be reported to Novartis within 24 hours of learning of its occurrence.
2. Any SAEs experienced after the 30 days period should only be reported to Novartis if the investigator suspects a causal relationship to study treatment.
3. Recurrent episodes, complications, or progression of the initial SAE must be reported as follow-up to the original episode, regardless of when the event occurs. This report must be submitted within 24 hours of the investigator receiving the follow-up information. An SAE that is considered completely unrelated to a previously reported one should be reported separately as a new event.

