1.2 Purpose

The effect of ligelizumab in patients with CSU inadequately controlled with H1-antihistamines was investigated in the Phase II dose-range finding study [CQGE031C2201] and demonstrated a dose-dependent response to ligelizumab and superior efficacy in multiple ligelizumab dose groups compared to the omalizumab treatment group. No safety concerns were identified in the ligelizumab groups. Two ongoing Phase III studies, [CQGE031C2302] and [CQGE031C2303], are intended to support the registration of ligelizumab for the treatment of patients with CSU in adolescents and adults inadequately controlled with H1-antihistamines.

There is relatively low number of Japanese subjects treated with the intended dose for registration or higher for 1 year in those Phase III studies above. Therefore, the purpose of this CQGE031C1301 study is to evaluate the safety and efficacy of ligelizumab in adult Japanese subjects with CSU, who remain symptomatic despite treatment with H1-antihistamines at locally-approved doses, over 12 months of treatment with ligelizumab and a post-treatment follow-up period of up to 12 weeks. It is a trial intended to support the registration of ligelizumab for the treatment of CSU in Japan.

2 Objectives and endpoints

[figure not shown]
Table 2-1 Objectives and related endpoints

3 Study design

This is a Phase III multi-center, open-label, single arm study. The study consists of 3 distinct periods:

- Screening period (Day -28 to Day -14): Duration of up to 4 weeks in which subjects who have given informed consent are assessed for eligibility.
- Treatment period (52 weeks): The subjects will be seen in the clinic every 4 weeks.
- Post-treatment follow-up period (12 weeks): This period consists of a subject visit in the clinic every 4 weeks with the final visit (Visit 1999) occurring 16 weeks after the last treatment dose.

Figure 3-1 Study design

Screening period

Subjects will have a screening period to establish eligibility for the study. Subjects will be required to attend 1 visit during screening period: Visit 1 (Day -28 to Day -14). An extended screening period will be permitted only in exceptional circumstances when information concerning eligibility is outstanding (eg, pending laboratory data).

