2.5.1 Primary endpoint

The primary variable is the number and percentage of patients who reported treatment emergent adverse events during the 64 week study period.

All adverse events which start after the first dose of study medication and within 16 weeks of the last dose will be considered as a treatment emergent adverse event.

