2.5.2 Statistical hypothesis, model, and method of analysis

The number of subjects who had a treatment emergent adverse event (events which started on or after the first dose of study treatment and within 16 weeks after the last study treatment, or events present prior to the first dose of study treatment but increased in severity based on preferred term within 16 weeks after the last study treatment) will be summarized overall, by system organ class (SOC) and preferred term descriptively. No statistical model will be applied for the primary endpoints.

All information obtained on adverse events will be displayed by subject.

All treatment emergent adverse events (TEAEs) during treatment period will also be summarized separately.

In addition to what is described in the primary endpoints section, treatment emergent adverse events with the number and percentage of patients having any adverse event overall, by system organ class and preferred term will be provided for:

- Serious treatment emergent adverse events (TESAEs)
- TEAEs by maximum severity
- TEAEs suspected by the investigator as study drug related
- TEAEs leading to permanent discontinuation of study drug

The number of subjects with TEAEs of special interest will be listed and summarized.

A subject with multiple adverse events within a primary system organ class is only counted once towards the total of the primary system organ class.

Unless otherwise specified, primary system organ classes will be sorted alphabetically and, within each primary system organ class, the preferred terms will be sorted in descending order of frequency. If a patient reported more than one adverse event with the same preferred term, the adverse event will be counted only once. If a patient reported more than one adverse event within the same primary system organ class, the patient will be counted only once at the system organ class level.

In addition, the most frequent TEAEs will be presented by preferred term in descending order of frequency.

For TEAEs by maximum severity, missing severity will be assumed to be severe in the summary table.

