2.7.2 Deaths

No separate listing or table will be provided from the database. Death will be reported as part of SAE which cause death.

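### For subjects who leave the study before Visit 1999, the last-visit cut-off for recording SAEs can keep SAEs and deaths inside the 16-week treatment-emergent window out of the analysis tables

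*Protocol*

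**What the plan says.** **Recording of SAEs.** Protocol 10.1.3 states: "Any SAEs reported up to the subject's last visit will be reported in the eCRF". The next sentence reads: "SAEs beyond that date will only be recorded in the Novartis Safety database". Every SAE must reach the sponsor until 30 days after the last study visit. Beyond that: "Any SAEs experienced after the 30 days period should only be reported to Novartis if the investigator suspects a causal relationship to study treatment".

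**Recording of AEs in general.** Protocol 10.1.1 requires adverse events to be recorded in the CRF, and monitoring to run for "at least 30 days following the last dose of study treatment or end of study visit, whichever is longer".

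**What the analysis counts.** SAP 2.5.1 takes as treatment-emergent "All adverse events which start after the first dose of study medication and within 16 weeks of the last dose". SAP 2.5.2 repeats the limit ("events which started on or after the first dose of study treatment and within 16 weeks after the last study treatment") and applies the treatment-emergent definition to the serious-event table. SAP 2.7.1.1 runs EAIR exposure time to the first event, the end of treatment plus 16 weeks, or week 64, whichever comes first. Leaving the study does not end it. On deaths, SAP 2.7.2 plans no separate table or listing: "Death will be reported as part of SAE which cause death".

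**When the last visit falls.** Protocol Section 3 describes follow-up "with the final visit (Visit 1999) occurring 16 weeks after the last treatment dose". Under Protocol 9.1.1, subjects who stop treatment early are expected at the treatment-discontinuation visit 4 weeks after the last dose and then at Visits 310 to 1999. Earlier study exit is foreseen after omalizumab use in follow-up (6.2.2, 9.1.1), withdrawal of consent (9.1.2), loss to follow-up (9.1.3) and sponsor termination (9.1.4).

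**The concern.** The recording limit is tied to the last visit and the counting limit to the last dose. When a subject's last visit falls before week 16 after the last dose, an SAE or death soon afterwards is treatment-emergent by the SAP's definition and reportable to the sponsor, yet 10.1.3 directs it away from the eCRF. Protocol 11.2 has the study database locked and then analysed, and neither document describes a merge or reconciliation with the safety database.

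This is a single-arm study with treatment-emergent adverse events as its primary variable. The events at risk are the serious ones. Their omission would lower the serious-TEAE table and the EAIR, and a fatal event could be absent from the planned outputs.

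**Working it through.** **1. The plan's own figures.** Table 8-1 puts the last dose on Day 337 and Visit 1999 on Day 449: 449 − 337 = 112 days = 16 weeks, as stated. Protocol 12.8.1 also reproduces: 65 × 0.90 = 58.5 (stated 58), and 1 − 0.97^100 = 0.952 (stated 95%). This point changes none of these.

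**2. Gap by last visit attended.** Gap = 112 − (days from last dose to last visit). In the first 30 days of a gap, every SAE is reportable but goes only to the safety database. After that, only suspected SAEs need be reported.

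| Last visit attended | Days after last dose | Days of window left | All SAEs reportable, not in eCRF | Only suspected SAEs reportable |
|---|---|---|---|---|
| Last dosing visit | 0 | 112 | 30 | 82 |
| EoT/TD | 28 | 84 | 30 | 54 |
| Visit 310 | 56 | 56 | 30 | 26 |
| Visit 320 | 84 | 28 | 28 | 0 |
| Visit 1999 | 112 | 0 | 0 | 0 |

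A subject last seen at EoT/TD has 84/112 = 75% of the window outside eCRF entry of SAEs. For 30/112 = 27% of it the sponsor is due every SAE.

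**3. Chance of missing an SAE.** The documents give neither the number of study leavers nor an SAE rate. Assumptions: k leavers, each last seen at EoT/TD, and r = 3 to 10 SAEs per 100 patient-years. Seven leavers is an upper assumption taken from 65 × 0.10 = 6.5. The probability of at least one missed SAE over d days each is 1 − exp(−r × k × d / 365.25).

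- k = 7, d = 30: 210 days = 0.575 patient-years. Expected 0.017 to 0.057 SAEs; probability 1.7% to 5.6%.
- k = 7, d = 84: 588 days = 1.610 patient-years. Expected 0.048 to 0.161 SAEs; probability 4.7% to 14.9%.
- k = 1, d = 84: 0.230 patient-years. Probability 0.7% to 2.3%.

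**4. Effect of one omission.** 1/65 = 1.5 percentage points.

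**5. EAIR denominator.** Planned person-time is 65 × 448 days = 29,120 days. Post-exit time that is credited without eCRF collection of SAEs is 84/29,120 = 0.3% for one leaver and 588/29,120 = 2.0% for seven. Any missed event leaves the numerator while this time stays in the denominator, so the EAIR moves slightly downward.

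**6. Protocol 10.1.1 against 10.1.3.** On day 10 after the last visit, 10.1.1 points to CRF recording of a mild AE, while 10.1.3 keeps an SAE or death on the same day out of the eCRF. An SAE is itself an adverse event under 10.1.2, so the two sections give opposite instructions for it.

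**The case against.** The best answer is that 10.1.3 says where SAEs are recorded, not what is tabulated. No sentence excludes safety-database SAEs from the tables, SAP 2.5.2 calls for by-subject display of the AE information obtained, and 10.1.1 can be read as requiring CRF entry. SAP 2.7.1.3 also counts deaths from serious TEAEs for the registries. This stands as far as it shows that loss is possible, not demonstrated. It does not remove the point: 10.1.3 says such SAEs go *only* to the safety database, and neither SAP section names another source.

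Four stronger readings are tempting, and the documents do not support them:

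- *Everyone who drops out is exposed, about 6 to 7 of 65.* The 10% in 12.8.1 converts enrolment into one-year exposure; it is not a study-exit rate. Subjects who only stop treatment are followed to Visit 1999 under 9.1.1, so their gap is zero.
- *Every early exit loses events because of this rule.* After withdrawal of consent the loss comes from 9.1.2. After loss to follow-up many SAEs would be unknown anyway, so only those learned of through later contact count. Sponsor termination is a contingency whose size cannot be stated.
- *SAEs that began before the last visit but were learned of later are lost too, even for completers.* This rests on one word about reporting. The following sentence can be read as referring to onset, and the protocol has AEs reconciled on the eCRF at the final visit.
- *One omission would be a large share of all serious events.* The documents give no expected SAE count, and the statement presumes that an event was missed.

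**Conclusion.** The point holds for a narrow group: subjects who leave the study before Visit 1999 and about whom the site still learns of SAEs. For them a stated rule, followed literally, can leave treatment-emergent SAEs or deaths held by the sponsor out of the serious-TEAE, EAIR and death outputs. Sections 10.1.1 and 10.1.3 also need to be reconciled with each other. Subjects who attend Visit 1999 are not affected.

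The expected loss is small: about 2% to 6% for at least one missed SAE over 30 days and 5% to 15% over 84 days, on the assumptions of seven leavers last seen at EoT/TD and 3 to 10 SAEs per 100 patient-years. With fewer leavers or later last visits it is smaller. A downward bias in the results is therefore a possibility, not a finding. It still merits correction, because one omitted subject is 1.5 percentage points in a 65-subject safety study and the remedy is cheap.

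**What to change.** 1. **Protocol 10.1.1 and 10.1.3.** Reconcile them so that any SAE with onset within 16 weeks after the last dose is entered in the eCRF, whatever the date of the last visit.
2. **Protocol 10.1.3.** Extend causality-independent SAE reporting to the later of 30 days after the last visit and 16 weeks after the last dose, where consent allows. Without this, a subject last seen at EoT/TD still has 54 days in which only suspected SAEs are collected, and moving those into the eCRF would mix complete with causality-selected reporting.
3. **SAP 2.5.2 and 2.7.2.** State that the safety database is reconciled with the study database at lock, and that all SAEs and deaths meeting the treatment-emergent definition enter the tables.
4. **SAP 2.7.1.1.** End EAIR exposure time at last contact for subjects who leave the study early.

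The cost is a few sentences, a small reconciliation at lock, and a longer SAE reporting duty for early leavers. No visits or procedures are added. The reported SAE rate may be slightly higher.
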